7.1.5.3.2. Sponsor Responsibility

If a serious unexpected adverse event is believed to be related to the IMP or study procedures, the sponsor will take appropriate steps to notify all investigators participating in sponsored clinical studies of TEV-50717 and the appropriate competent authorities (and IEC/IRB, as appropriate).

In addition to notifying the investigators and competent authorities (and IEC/IRB, as appropriate), other action may be required, including the following:

- altering existing research by modifying the protocol
- discontinuing or suspending the study

- modifying the existing consent/assent form and informing all study participants of new findings
- modifying listings of expected toxicities to include adverse events newly identified as related to TEV-50717

7.1.6. Protocol-Defined Adverse Events of Special Interest

No protocol-defined adverse events of special interest were identified for this study.

7.1.7. Withdrawal Due to an Adverse Event

Any patient who experiences an adverse event may be withdrawn from the study or from study treatment at any time at the discretion of the investigator. If a post-baseline QTcF value >500 msec or change from baseline >60 msec is found, the investigator should repeat the ECG assessment twice and compare the average of the 2 pre-treatment QTcF values (baseline and screening) to the average of the 3 post-baseline QTcF values. The IMP must be stopped for any confirmed post-baseline QTcF value >500 msec or increase from baseline >60 msec. If a patient is withdrawn wholly or in part because of an adverse event, both the adverse events page and termination page of the CRF will be completed at that time.

In addition, a blood sample should be obtained for the measurement of IMP concentrations, if possible. The patient will be monitored at the discretion of the investigator (eg, until the event has resolved or stabilized, until the patient is referred to the care of a health care professional, or until a determination of a cause unrelated to the IMP or study procedure is made). The investigator must inform the clinical project physician/clinical leader as soon as possible of any patients who are being considered for withdrawal due to adverse event(s). Additional reports must be provided when requested.

If a patient is withdrawn from the study for multiple reasons that include adverse events, the termination page of the CRF should indicate that the withdrawal was related to an adverse event. An exception to this requirement will be the occurrence of an adverse event that, in the opinion of the investigator, is not severe enough to warrant discontinuation but that requires the use of a prohibited medication, thereby requiring discontinuation of the patient. In such a case, the reason for discontinuation would be need to take a prohibited medication, not the adverse event.

7.1.8. Protocol Deviations Because of an Adverse Event

If a patient experiences an adverse event or medical emergency, deviations from the protocol may be allowed on a case-by-case basis. To ensure patient safety, after the event has stabilized or treatment has been administered (or both), the investigator or other physician in attendance must contact the physician identified in the Clinical Study Personnel Contact Information section of this protocol as soon as possible to discuss the situation. The investigator, in consultation with the sponsor, will decide whether the patient should continue to participate in the study.

7.2. Psychometric Rating Scales

Site-administered safety scales include the MINI Kid and C-SSRS, and self-administered safety scales include CDI-2.

7.2.1. Mini International Neuropsychiatric Interview for Children and Adolescents

Select MINI Kid modules are administered at screening only. Children 13 years of age and under may be interviewed separately or jointly with the caregiver/adult as appropriate or defined by the scale. For children over 13 years of age, caregiver/adult involvement is strongly encouraged. Questions should be directed to the child, but the caregiver/adult should be encouraged to add relevant information.

The MINI Kid is a short questionnaire to be administered by a trained clinician. The MINI Kid assesses symptoms of psychiatric disorders as outlined in the International Classification of Diseases-10 and the DSM-V™ in children 6 to 17 years of age by self-report. For children under 13 years old, the patient may be interviewed separately or jointly with the caregiver/adult as appropriate or defined by the scale, and the caregiver/adult is encouraged to participate when needed. The MINI Kid version 6 is composed of 24 modules overall, and questions are largely yes-or-no questions. The current study will focus on 8 modules: Major Depressive Episode (Module A), (Hypo) Manic Episode (Module D), OCD (Module J), Alcohol Dependence/Abuse (Module L), Substance Dependence/Abuse (Non-alcohol; Module M), ADHD (Module O), Conduct Disorder (Module P), and Psychotic Disorders and Mood Disorders with Psychotic Features (Module R).

A reference sample is provided in [Appendix I](#).

7.2.2. Columbia-Suicide Severity Rating Scale

The C-SSRS children's baseline/screening scale assesses past and current suicidal ideation and behaviors to determine suicide risk and is administered at screening. C-SSRS children's SLV scale is administered at baseline and at weeks 2, 4, 8, and 9. Children 13 years of age and under may be interviewed separately or jointly with the caregiver/adult as appropriate or defined by the scale. For children over 13 years of age, caregiver/adult involvement is strongly encouraged. Questions should be directed to the child, but the caregiver/adult should be encouraged to add relevant information. The C-SSRS is an interview by trained study personnel.

Suicidal ideation

- Patients with a positive C-SSRS suicidal ideation score on either items 1 or 2 or a change on the CDI-2 Parent or Self-Report Profiles consistent with increasing depressive symptoms must be 1) discussed with the medical monitor, 2) re-evaluated within 2 to 3 days in a clinic visit, and 3) treated according to the investigator's medical judgment. Consultation with a child and adolescent psychiatrist or licensed child/adolescent mental health provider is advised, followed by close ongoing monitoring.
- If patients endorse or report a C-SSRS suicidal ideation level of 3, 4, or 5, subjects will be evaluated immediately by the study investigator and referred for psychiatric evaluation. The medical monitor will be immediately consulted. If it is determined by the investigator, after consultation with the medical monitor and the consulting psychiatrist, that exposure to the IMP may have contributed to this change in C-SSRS and/or increased depressive symptoms, IMP will be immediately discontinued and the patient terminated from the study. In cases where it is determined that IMP did not contribute to changes in depression or suicidality, the investigator will consult with

the medical monitor, the consulting psychiatrist, and/or sponsor to determine whether the patient should continue in the study.

Suicidal behavior

- Actual attempt:
 - If patients report any suicidal behavior that is an actual attempt as assessed in the C-SSRS, they will be evaluated immediately by the study investigator, referred for psychiatric evaluation, and terminated from the study.
- Interrupted attempt, aborted attempt, or Preparatory Acts or Behavior:
 - If patients report any suicidal behavior that is interrupted, aborted, or preparatory as assessed in the C-SSRS, they will be evaluated immediately by the study investigator and referred for psychiatric evaluation. In cases where it is determined in the psychiatric evaluation that IMP did not contribute to changes in suicidal behavior, the investigator will consult with the medical monitor, the consulting psychiatrist, and/or sponsor to determine whether the patient should continue in the study.

A reference sample is provided in [Appendix K](#).

7.2.3. Children’s Depression Inventory, Second Edition

The CDI-2 (Parent and Self-report Profiles) is administered at screening; baseline; and weeks 2, 4, 8, and 9. As the CDI-2 is designed for children 7 to 17 years of age, children 6 years of age at baseline will not complete the self-report version; the caregiver/adult will complete the parent version.

The CDI-2 Self-report is a 28-item self-report questionnaire assessing depressive symptoms in children 7 to 17 years of age with basic reading and comprehension skills. In the CDI-2, children are asked to choose 1 of 3 statements that most closely aligns with their feelings in the previous 2 weeks. The questionnaire covers both the major and minor symptoms of depression as outlined in the Diagnostic and Statistical Manual of Mental Disorders, Fourth Edition, Text Revision ([Sun and Wang 2015](#)).

The CDI-2 Parent is a 17-item questionnaire administered to parents to assess depression-related behaviors observed in their children. In the CDI-2 Parent, parents are asked to rate their child’s behaviors in the past 2 weeks on a 4-point Likert scale from “not at all” to “much or most of the time”. The questionnaire allows for the division of depressive symptoms into functional problems and emotional problems ([Sun and Wang 2015](#)).

A reference sample is provided in [Appendix J](#).

7.3. Pregnancy

Any female patient becoming pregnant during the study will discontinue IMP.

All pregnancies of female patients participating in the study that occur during the study, or within 14 days after the end of the study, are to be reported immediately to the individual identified in the Clinical Study Personnel Contact Information section of this protocol, and the investigator must provide the sponsor (LSO/CRO) with the completed pregnancy form. The

process for reporting a pregnancy is the same as that for reporting a serious adverse event but using the pregnancy form (see Section 7.1.5.3).

The investigator is not required to report patients who are found to be pregnant between screening and baseline, provided no IMP was given. All female patients who become pregnant will be monitored for the outcome of the pregnancy (including spontaneous, elective, or voluntary abortion). If the pregnancy continues to term, the outcome (health of the infant up to 8 weeks of age), including details of birth and presence or absence of any birth defect, congenital abnormalities, or maternal and newborn complications, will be reported to the sponsor. Any complication of pregnancy during the study and any complication of pregnancy that the investigator becomes aware of after withdrawal from the study will be reported as an adverse event or serious adverse event, as appropriate.

If the pregnancy in the female patient participating in the study does not continue to term, 1 of the following actions will be taken:

- For a spontaneous abortion, report as a serious adverse event.
- For an elective abortion due to developmental anomalies, report as a serious adverse event.
- For an elective abortion **not** due to developmental anomalies, report on the pregnancy form; do not report as an adverse event.

7.4. Medication Error and Special Situations Related to the Investigational Medicinal Products

Any administration of IMP that is not in accordance with the study protocol should be reported on the CRF either as a violation, if it meets the violation criteria specified in the protocol ([Appendix C](#)), or as a deviation, in the patients source documents, regardless of whether or not an adverse event occurs as a result.

The following are types of medication errors and special situations:

1. Medication error: Any unintentional error in the prescribing, dispensing, or administration of a medicinal product while in the control of the healthcare professional, patient, or consumer.
2. Overdose: Administration of a quantity of a medicinal product given per administration or cumulatively which is above the maximum recommended dose according to the authorized product information. Clinical judgment should always be applied. Any dose of IMP (whether the test IMP or placebo), whether taken intentionally or unintentionally, in excess of that prescribed must be immediately reported to the sponsor.
3. Misuse: Situations where the IMP is intentionally and inappropriately used not in accordance with the authorized product information.
4. Abuse: Persistent or sporadic, intentional excessive use of IMP which is accompanied by harmful physical or psychological effects.
5. Off-label use: Situations where an IMP is intentionally used for a medical purpose not in accordance with the authorized product information.

6. Occupational exposure: Exposure to an IMP, as a result of one’s professional or non-professional occupation.
7. Breastfeeding: Suspected adverse reactions which occur in infants following exposure to a medicinal product from breast milk.

7.5. Clinical Laboratory Tests

All clinical laboratory test results outside of the reference range will be judged by the investigator as belonging to one of the following categories:

- abnormal and not clinically significant
- abnormal and clinically significant

The clinical significance of the laboratory value will be evaluated by the criteria described in the laboratory manual and by the judgement of the investigator. A laboratory test result that is judged by the investigator as clinically significant will be recorded both on the source documentation and the CRF as an adverse event, and monitored as described in Section 7.1.2. An event may include a laboratory or diagnostic test abnormality (once confirmed by repeated testing) that results in the withdrawal of the patient from the study, the temporary or permanent withdrawal of IMP, or further diagnostic work-up. (Note: Abnormal laboratory or diagnostic test results at the screening visit that preclude a patient from entering the study or receiving IMP are not considered adverse events.).

Table 6: Clinical Laboratory Tests

Serum Chemistry	Hematology	Urinalysis
calcium	hemoglobin	protein
phosphorus	hematocrit	glucose
sodium	red blood cell (RBC) count	ketones
potassium	mean cell volume	blood (hemoglobin)
chloride	platelet count	pH
creatinine	white blood cell (WBC) count, and differential count	specific gravity
glucose	– Absolute neutrophil count (ANC)	microscopic
magnesium	– polymorphonuclear leukocytes (neutrophils)	– bacteria
BUN	– lymphocytes	– RBCs
total cholesterol	– eosinophils	– WBCs
uric acid	– monocytes	– casts
Alanine aminotransferase (ALT)	– basophils	– crystals
Aspartate aminotransferase (AST)		
Lactate dehydrogenase (LDH)		
Alkaline phosphatase (ALP)		
bicarbonate or carbon dioxide		
total protein		
albumin		
total bilirubin		
direct bilirubin		

7.5.1. Serum Chemistry, Hematology, and Urinalysis

Clinical laboratory tests (serum chemistry, hematology, and urinalysis) will be performed at the time points detailed in [Table 2](#). Clinical laboratory tests will be performed using the central laboratory. Specific laboratory tests to be performed are provided in [Table 6](#).

7.5.2. Other Clinical Laboratory Tests

7.5.2.1. Human Chorionic Gonadotropin Tests

β-HCG tests in serum or urine will be performed for all females who are postmenarchal or ≥12 years of age as detailed in [Table 2](#) and, if clinically indicated. Any female patient who becomes pregnant during the study will be withdrawn. Procedures for reporting the pregnancy are provided in Section [7.3](#).

7.5.2.2. Urine Drug Screen

A urine drug screen (UDS) will be performed at the time points specified in [Table 2](#). The UDS detects the presence of drugs prohibited according to the laboratory manual. If a given parameter cannot be tested using urine, an alternative matrix (eg, serum) may be considered acceptable. The sponsor’s medical expert must be made aware in advance of, and provide approval for, drug screen parameters to which this will apply.

A positive result for any of the above drugs or their metabolites, without medical explanation, will preclude the patient from enrollment or continued participation in the study.

7.5.2.3. Cytochrome P450 2D6 Genotyping

One 3-mL sample for CYP2D6 genotyping will be collected from all patients in the study at screening. Sample testing results will not be provided to the study team until the study is unblinded.

This assessment potentially includes the association analysis of the variation in CYP2D6 gene with clinical treatment responses to the IMP (eg, efficacy, pharmacokinetic, tolerability, and safety features or disease susceptibility and severity features).

7.6. Physical Examinations

Physical examination, including height and weight, general appearance, skin, head, eyes, ears, nose, throat, neck, lymph nodes, cardiovascular, respiratory, musculoskeletal, abdominal, and extremities will be performed at the time points detailed in [Table 2](#).

Weight must be measured with shoes and outerwear off.

Any physical examination finding that is judged by the investigator as a clinically significant (except at the screening visit) will be considered an adverse event, recorded on the CRF, and monitored as described in [Section 7.1.2](#).

7.7. Vital Signs

Vital signs (pulse, BP, body temperature, and respiratory rate) will be measured at the time points detailed in [Table 2](#). All vital signs results outside of the reference ranges will be judged by the investigator as belonging to one of the following categories:

- abnormal and not clinically significant
- abnormal and clinically significant

Before BP and pulse are measured, the patient must rest in a supine or semi-erect/seated position for at least 5 minutes. (The same position and arm should be used each time vital signs are measured for a given patient.) For any abnormal vital sign value, the measurement should be repeated as soon as possible. Any vital sign value that is judged by the investigator as clinically significant will be recorded both on the source documentation and the CRF as an adverse event, and monitored as described in [Section 7.1.2](#).

7.8. Electrocardiography

A 12-lead ECG will be recorded at the time points detailed in [Table 2](#). All ECGs will be performed after at least 5 minutes rest in a supine or semi-supine position. A qualified physician at a central diagnostic center will be interpreting the ECG.

All ECG results outside of the reference ranges will be judged by the investigator as belonging to one of the following categories:

- abnormal and not clinically significant
- abnormal and clinically significant

Any ECG finding that is judged by the investigator as clinically significant (except at the screening visit) will be considered an adverse event, recorded on the source documentation and in the CRF, and monitored as described in [Section 7.1.2](#).

If a post-baseline QTcF value >500 msec or change from baseline >60 msec is found, the investigator should repeat the ECG assessment twice and compare the average of the 2 pre-treatment QTcF values (baseline and screening) to the average of the 3 post-baseline QTcF values. The IMP must be stopped for any confirmed post-baseline QTcF value >500 msec or increase from baseline >60 msec.

7.9. Assessment of Suicidality

TEV-50717 is considered to be central nervous system (CNS)-active. In addition, there have been some reports of suicidal ideation or behavior as reported in the product label when it has been given to some patients with certain conditions. The sponsor considers it important to monitor for such events before and during this clinical study.

Some CNS-active IMPs may be associated with an increased risk of suicidal ideation or behavior when given to some patients with certain conditions. Although this IMP or other similar medicinal products in this class have not been shown to be associated with an increased risk of suicidal thinking or behavior when given to this study population, the sponsor considers it important to monitor for such events before or during this clinical study.

The study population being administered TEV-50717 should be monitored appropriately and observed closely for suicidal ideation and behavior or any other unusual changes in behavior. Consideration should be given to discontinuing TEV-50717 in participants who experience signs of suicidal ideation or behavior; detailed recommendations are provided in [Section 7.2.2](#).

Baseline assessment of suicidal ideation and behavior and treatment-emergent suicidal ideation and behavior will be assessed during the study using the Columbia-Suicide Severity Rating Scale described in [Section 7.2.2](#).

Depression and Suicidality as an Adverse Event

Families and caregivers of subjects will be instructed to monitor patients for any changes in or new onset of depressive symptoms; unusual changes in mood, cognition, or behavior; or onset of and/or changes in suicidal ideation or behavior, and to report such symptoms immediately to the study investigator. Telephone contacts and clinic visits also allow opportunities for investigators to assess adverse events.

If a relevant change in status is identified, patients will be seen immediately for an unscheduled visit by the study investigator and discussed with the medical monitor. The patient will be referred for further psychiatric evaluation if there is any suspected suicidal ideation with any level of intent, suicidal behavior, or clinical findings suggesting that the patient may be dangerous to self or others, and/or experiencing depression. The investigator will record these symptoms as an adverse event of depression and/or suicidality. If it is determined by the investigator, after consultation with the medical monitor and the consulting psychiatrist, that exposure to the IMP may have contributed to the adverse event of depression or suicidality, IMP will be immediately discontinued and the patient will be terminated from the study. Follow up with a pediatric psychiatrist or licensed child and adolescent mental health clinician will be arranged.

In cases where it is determined that IMP did not contribute to the adverse event of depression or suicidality, the investigator will consult with the medical monitor and/or sponsor to determine whether the patient should continue in the study.

A reference sample is provided in [Appendix K](#).

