At the discretion of the investigator, the screening visit may be divided into 2 visits to reduce the burden on patients. If the screening visit is divided into 2 visits, the blood sample should be obtained during the first of the 2 visits. Patients will return to the clinic on day 1 for baseline procedures and to re-confirm eligibility. Patients may be rescreened 1 time if there is a change in the status of the patient regarding eligibility for the study. (Note: Details of rescreening must be approved and documented by the medical monitor and/or Clinical Surveillance and Training [CST] team.)

Treatment period (8 weeks): Patients who continue to remain eligible for participation in the study will be randomized at the baseline visit (day 1) and will receive blinded IMP to begin that same day (day 1). Tablets should be taken with food (eg, a snack) and should not be taken on an empty stomach. Patients and their caregiver/adult will interact regularly with the clinical research staff, either by telephone contact or clinic visit to assure adherence with study procedures and to evaluate safety and efficacy. To this end, clinic visits will be performed at weeks 2, 4, and 8 after baseline to evaluate safety; assess tic severity with the YGTSS, TS-CGI, TS-PGII, and the C&A-GTS-QOL; and perform safety rating scales to augment adverse event reporting, concomitant medication usage, clinical laboratory examination, and 12-lead ECGs. Telephone contacts will occur at the end of weeks 1, 3, 6, and 7.

As this is a fixed-dose study, patients will undergo dose escalation (ie, forced titration) to their target dose over the first 4 weeks of treatment. If a patient experiences depression, suicidal ideation or behavior, anxiety, akathisia, parkinsonism, or somnolence, or any other adverse event that interferes with daily activity, or any adverse event that is related to IMP, a single dose reduction is permitted. The investigator must discuss any further dose adjustments (eg, holding the dose or doses) with the medical monitor.

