3.4. Drug Administration

IMP will be administered as follows:

- IMP should be swallowed whole and taken with food (eg, a snack) and should not be taken on an empty stomach.
- Dosing will be based on body weight and CYP2D6 impairment status at the baseline visit, as shown in Table 1.
- The total daily dose, as provided in Table 1, is divided into a twice-daily administration. Two tablets will be taken twice daily starting at day 1 per Table 1. Daily doses will be administered twice daily, approximately 8 to 10 hours apart during the day. Depending on the dose and arm assigned, TEV-50717 tablets and/or placebo tablets will be taken to maintain the blind. A minimum of 6 hours should elapse between doses. If a patient misses a dose, and it is within 6 hours of their next dose, the missed dose should be skipped.
- After week 1, dose escalations may not occur more frequently than once every 5 days.
- The dose of IMP will be escalated weekly during the escalation period, according to Table 1.
- In the case of an adverse event, the investigator is permitted to perform a single dose reduction of 6 mg. **The investigator must discuss any further dose adjustments (eg, holding the dose or doses) with the medical monitor.**
- During the titration period, the dose of the IMP will be adjusted weekly according to Table 1. Investigators will be blinded to CYP status, with a dose cap for poor metabolizers prespecified by the IRT.

IMP will be packaged in blister packs and provided for patients to take at home (see Section 5.1).

Table 1: Daily Dose of IMP by Baseline Body Weight Category, CYP2D6 Impairment, and Study Week

Dose group Baseline weight (kg)	Daily dose (mg) at the start of visit/week ^a			
	Week 1 (Days 1-7)	Week 2 (Days 8-14)	Week 3 (Days 15-21)	Week 4 main dose (Days 22-28) to Week 8 main dose (Days 50-56)
Low dose				
≥40	12	24	30	36
≥40, CYP impaired	6	12	18	18
30 to <40	6	12	18	24
30 to <40, CYP impaired	6	12	12	12
20 to <30	6	12	18	18
20 to <30, CYP impaired	6	6	6	6
High dose				
≥40	12	24	36	48
≥40, CYP impaired	6	15	24	30
30 to <40	12	24	30	36
30 to <40, CYP impaired	6	12	18	18
20 to <30	12	18	24	30
20 to <30, CYP impaired	6	12	12	12

^a Administration of a given dose will take place throughout the days indicated. The new dose starts the morning after the telephone contact or the morning after the clinic visit.

CYP impaired=patients who are receiving a strong CYP2D6 inhibitor or who are a CYP2D6 poor metabolizer.

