5.1.1.2. Dose Modification and Dose Stratification

As this is a fixed dose study, patients will undergo dose escalation (ie, forced titration) to their target dose over the first 4 weeks of treatment (see Section 3.4 and Table 1). If a patient experiences depression, suicidal ideation or behavior, anxiety, akathisia, parkinsonism, or somnolence, or any other adverse event that interferes with daily activity, or any adverse event that is related to IMP, a single dose reduction is permitted. The investigator must discuss any further dose adjustments (eg, holding the dose or doses) with the medical monitor.

In case of such an adverse event, the investigator will determine if a dose reduction or suspension is necessary. If a determination is made that a dose reduction or suspension is required, the medical monitor must be contacted. All available information, including the patient and caregiver/adult reports of adverse events, the clinical assessment of safety by the investigator, and information from rating scales should be incorporated in the decision. This reduced dose will become the patient's dose for the remainder of the study.

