5.8. Temporary Discontinuation of Investigational Medicinal Product

Dose Reduction

If a patient experiences a “clinically significant” adverse event that is attributed to IMP, the investigator will determine if a dose reduction or suspension is necessary. Dose adjustments should be made based on all available information, including the patient and caregiver/adult reports of adverse events and tic reduction, the clinical assessment of safety and efficacy by the investigator, and information from rating scales. In the case of an adverse event, the investigator is permitted to perform a single dose reduction of 6 mg. **The investigator must discuss any further dose adjustments (eg, holding the dose or doses) with the medical monitor.**

If the determination that a patient requires a dose reduction or suspension is made during a telephone contact, an unscheduled clinic visit should be conducted as soon as practicable thereafter.

Dose Suspension

Suspension of study medication for up to 1 week, if warranted for patient safety, is allowed. If the patient restarts study medication within 7 days of suspension, the full dose of TEV-50717 may be resumed without titration. **Suspensions of study medication for adverse events must be reviewed with the medical monitor before therapy is restarted.** If a subject’s serum potassium or magnesium were tested and found to be below the lower limit of normal and clinically significantly, the laboratory test should be repeated at least once. If the abnormality in the repeated laboratory test is consistent with the prior laboratory test, the IMP must be suspended. The Medical Monitor must be contacted to determine the appropriate investigation and treatment. TEV-50717 may only be restarted once serum potassium or magnesium have normalized.

The reason for a dose reduction or suspension must be clearly documented.

If a dose reduction or suspension occurs before a scheduled clinic visit, the clinic visit will be postponed so that efficacy evaluations can be performed at least 5 days after the change.

The patients who restart IMP treatment will follow the visit schedule as outlined in [Table 2](#). Patients who withdraw from the study will proceed as described in [Section 4.3](#).

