#### **3.1. Primary Estimand**

The primary estimand is the difference in means between TEV-50717 high dose and placebo for the change in the Total Tic Score (TTS) of the Yale Global Tic Severity Scale (YGTSS) from baseline to week 8, in the target patient population of children and adolescents with TS who receive at least 1 dose of IMP and have both a baseline and at least 1 post-baseline YGTSS assessment, regardless of whether or not dose reduction, suspension, or treatment discontinuation occurred, and regardless of treatment-related adverse events. For the intercurrent event of study discontinuation, all data collected until time of study discontinuation will be included and a missing at random (MAR) assumption will be hypothesized.

The primary estimand assesses the effectiveness in the reduction of motor and phonic tics associated with TS, focusing on the causal effects attributable to the investigational medicinal product (IMP).

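### For depression or suicidality attributed to study drug, the dose-modification sections permit a dose reduction with continued participation, while Protocol 7.9 requires discontinuation and study termination; nothing reconciles them

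*Protocol*

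**What the plan says.** **Dose-modification text.** Protocol 5.1.1.2, repeated in the synopsis and Section 3.1, opens its list of triggers with "If a patient experiences depression, suicidal ideation or behavior, anxiety, akathisia, parkinsonism, or somnolence". The list goes on to other events that interfere with daily activity and ends, in the wording of Section 3.1, "or any adverse event that is related to IMP, a single dose reduction is permitted". The medical monitor must be contacted when a reduction or suspension is needed, and the lowered dose becomes the patient's "dose for the remainder of the study". Section 5.8 says that for a clinically significant "adverse event that is attributed to IMP, the investigator will determine if a dose reduction or suspension is necessary". Section 3.4 adds that in the case of an adverse event "the investigator is permitted to perform a single dose reduction of 6 mg"; any further adjustment has to be discussed with the medical monitor.

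**Suicidality text.** Section 7.9 provides that if the investigator, after consulting the medical monitor and the consulting psychiatrist, determines that exposure to study drug "may have contributed to the adverse event of depression or suicidality, IMP will be immediately discontinued and the patient will be terminated" from the study. Where study drug did not contribute, continuation is left open. Section 7.2.2 has a parallel rule for C-SSRS ideation levels 3 to 5: if exposure "may have contributed to this change in C-SSRS and/or increased depressive symptoms, IMP will be immediately discontinued" and participation ends.

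**SAP.** The primary estimand in SAP 3.1 counts outcomes whether or not the dose was reduced. "For the intercurrent event of study discontinuation, all data collected until time of study discontinuation will be included", with missing at random assumed thereafter. SAP 9.4 plans separate adverse-event tables for dose reduction and for study drug discontinuation.

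**The concern.** The two sets of rules cover the same event and lead to opposite results. On one route the child stays in the trial on a lower dose; on the other, drug stops and participation ends. A site that follows 5.1.1.2 or 5.8 as written would breach 7.9.

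The patients are 6 to 16 years old and the event is a psychiatric safety event, so the required action should be stated once. Differing readings also affect the data. The same event could enter the analysis as a dose reduction with observations continuing to week 8, or as study discontinuation handled under missing at random. It could also be tabulated under either action taken.

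Two smaller inconsistencies sit in the same text. First, a 6 mg reduction is not a reduction where the scheduled dose is 6 mg/day. Second, SAP 3.8 contemplates more than one 6 mg reduction with the medical monitor notified, whereas the protocol gives the investigator one reduction and requires discussion of anything further.

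**Working it through.** **Step 1: set the rules side by side for an event of depression or suicidality attributed to study drug.**

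| Section | Does the event trigger it? | Action |
|---|---|---|
| Synopsis, 3.1, 5.1.1.2 | Yes, by name and again as a drug-related event | One reduction permitted; patient continues at that dose |
| 5.8 | Yes, if clinically significant | Investigator decides on reduction or suspension |
| 7.9 | Yes; possible contribution is enough | Immediate discontinuation and study termination |
| 7.2.2 | Yes, for C-SSRS ideation 3 to 5 | Immediate discontinuation and study termination |

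The overlap follows from the protocol's own definitions. Table 5 (Section 7.1.4) classes an event as related when a link to study drug cannot be excluded with certainty. An event so classed also fits the possible-contribution threshold in 7.9.

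**Step 2: look for a passage that resolves it.**
- Sections 3.1, 3.4, 5.1.1.2 and 5.8 neither exempt these events nor refer to 7.2.2 or 7.9.
- Section 7.9 refers only to 7.2.2.
- The withdrawal cross-references in Section 4.3 list neither 7.2.2 nor 7.9.
- Section 7.1.7 makes withdrawal for an adverse event discretionary.
- An earlier paragraph of 7.9 asks only that discontinuation be considered.
- Section 7.2.2 leaves C-SSRS items 1 and 2, and CDI-2 worsening, to the investigator's judgment after discussion with the medical monitor.

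No precedence rule was found. The last two items add to the inconsistency.

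**Step 3: size of the effect.** The documents give no event rate. Assume 1 to 3 patients per 50-patient arm.

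- Safety tables: 1/50 = 2.0 percentage points; 3/50 = 6.0 percentage points.
- Primary contrast, supposing each such patient's week 8 value changed by the full design difference of 6.5 (Protocol 9.1): 6.5 × 1/50 = 0.13; 6.5 × 3/50 = 0.39.
- Design standard error, with SD 9.5 and 50 per arm: 9.5 × √(2/50) = 1.90.
- Ratios: 0.13/1.90 = 0.07; 0.39/1.90 = 0.21.
- Context: SAP 8.2.2 reports 8% all-cause early termination. Applied to the 150 planned patients, 0.08 × 150 = 12. Terminations under 7.9 would be a subset of these.

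**Step 4: the 6 mg decrement against Table 1.** Subtracting 6 mg leaves 0 mg/day in these rows:

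| Period | Low dose (6 rows) | High dose (6 rows) | Total |
|---|---|---|---|
| Week 1 | 5 | 3 (all CYP impaired) | 8 of 12 |
| Week 2 | 1 | 0 | 1 of 12 |
| Week 3 | 1 | 0 | 1 of 12 |
| Weeks 4 to 8 | 1 | 0 | 1 of 12 |

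The row that remains from week 2 onward is low dose, 20 to <30 kg, CYP impaired. It is outside the primary high-dose comparison.

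**The case against.** The strongest reply is that the rules can be read together. The dose-modification text is permissive and 7.9 is mandatory and more specific. A site that follows 7.9 never breaches 5.1.1.2, and naming depression as a ground for reduction keeps a purpose for cases where study drug did not contribute. That reading is available, but no passage states it. It also sits badly with 5.1.1.2, whose trigger sentence expressly reaches drug-related events, and with 5.8, which is confined to events attributed to study drug.

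Several limiting points stand:
- Medical-monitor contact is required on both routes, which reduces variation between sites. It does not remove it, because the monitor works from the same text.
- The protocol refers to a safety monitoring plan that is not among the documents, so how such events were routed in practice is unknown.
- The overall adverse-event tables, the suicide/self-injury and depression SMQs, and the CDI-2 and C-SSRS summaries do not depend on the action taken. Only the action-taken tables would differ.
- Early-termination YGTSS data may be mapped to a visit under SAP 6.4, so a missing week 8 value is not automatic.
- The SAP 3.8 difference is narrow, notification against discussion, and the SAP does not direct dosing at sites.
- Holding or suspending doses with medical-monitor involvement remains possible in the 6 mg/day rows.

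**Conclusion.** The concern holds. For depression or suicidality attributed to study drug, the protocol gives two incompatible actions and no means of choosing between them. The conflict is confined to attributed events; for others, 7.9 leaves continuation open.

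The statistical effect is small: 0.07 to 0.21 of the design standard error on the primary contrast, and 2 to 6 percentage points of an arm between two safety tables. Both ranges rest on the assumed 1 to 3 patients per arm, and the first also on a full 6.5-point change in each. The weight of the finding is in safety conduct and reporting in children. It should be corrected, but it does not threaten the primary result.

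**What to change.** - Reconcile Sections 3.1, 3.4, 5.1.1.2 and 5.8 (and the synopsis) with 7.2.2 and 7.9, so that one stated action applies to depression or suicidality attributed to study drug. Add cross-references in both directions. The same edit can cover the softer paragraph in 7.9 and the lower C-SSRS and CDI-2 tier in 7.2.2.
- Reconcile the 6 mg decrement with the 6 mg/day cells of Table 1.
- Align SAP 3.8 with the reconciled protocol text.

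Which clinical rule applies is for the sponsor's clinical team to decide. The cost is clarification or amendment text, a site memo and one SAP correction, with no extra patients or procedures.
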